5.1.2 Secondary Endpoints

Not applicable.

5.2 ASSESSMENT OF EFFICACY

Measurements of FVC

Unique spirometry devices (identical to the ones used in the parent studies) will be supplied to all participating sites at trial initiation and spirometry performance will be centrally reviewed. During the course of the trial and specifically at each interim analysis, the sponsor will re-evaluate the use of central spirometry. If applicable, i.e. central spirometry will be no longer used, measurements of FVC will be performed using calibrated electronic spirometers at the investigational site or at a referral site.

Spirometers and usage of spirometers must meet ATS/ERS criteria ([P05-12782](#)), including daily calibration of the spirometer, and regular calibration of the calibration pump. Spirometry will be conducted while the patient is in a seated position. The test will be done in

Proprietary confidential information.

© 2017 Boehringer Ingelheim International GmbH or one or more of its affiliated companies. All rights reserved.

This document may not - in full or in part - be passed on, reproduced, published or otherwise used without prior written permission.

triplicate and selection of the best result done according to the guidelines. Spirometric results captured by spirometers provided by the sponsor will be electronically transmitted and confirmed by central reading.

For each patient, pulmonary function testing will always start at approximately the same time of the day (with ± 60 minutes maximum difference, time will be recorded). On days of clinic visits, patients must refrain from strenuous activity at least 12 hours prior to pulmonary function testing.

Smoking should be discouraged throughout the study day (clinic visit) and will not be permitted in the 30-minute period prior to spirometry. Patients should also avoid cold temperatures, environmental smoke, dust, or areas with strong odours (e.g., perfumes).

Definition of Acute IPF Exacerbations

Otherwise unexplained clinical features within one month, including all of the following:

- Unexplained worsening or development of dyspnoea within 30 days;
- New diffuse pulmonary infiltrates on chest X-ray, and/or new HRCT parenchymal abnormalities with no pneumothorax or pleural effusion (new ground-glass opacities) since last visit;
- Exclusion of infection as per routine clinical practice and microbiological studies;
- Exclusion of alternative causes as per routine clinical practice, including:
 - left heart failure,
 - pulmonary embolism,
 - identifiable cause of acute lung injury.

Acute IPF exacerbations will be collected as adverse events.

5.3 ASSESSMENT OF SAFETY

5.3.1 Physical examination

Physical examination includes assessment of heart, lung, abdomen and measurement of weight. Abnormal findings in the parent trial which were recorded as an adverse event and are still ongoing at the time of screening, as well as any new abnormal finding at the time of screening, will be recorded as baseline conditions on the appropriate eCRF page. New abnormal findings or worsening of baseline conditions detected at the subsequent physical examinations will be recorded as adverse events on the appropriate eCRF page.

Proprietary confidential information.

© 2017 Boehringer Ingelheim International GmbH or one or more of its affiliated companies. All rights reserved.

This document may not - in full or in part - be passed on, reproduced, published or otherwise used without prior written permission.

5.3.2 Vital signs

Vital signs including measurements of systolic and diastolic blood pressure and pulse rate, will be measured with the patient seated after having rested for at least 5 minutes at each on site visit.

5.3.3 Safety laboratory parameters

The laboratory tests will include:

- Haematology: red blood cell count, haemoglobin, haematocrit, mean corpuscular volume, white blood cell count including differential, platelet count.
- Chemistry: creatinine, AST, ALT, total protein, alkaline phosphatase, total bilirubin.
- Coagulation: International normalized ratio (INR) and partial thromboplastin time (PTT).

If laboratory values indicate toxicity, adequate and more frequent blood sampling will be performed at the discretion of the investigator.

Laboratory analysis during main visits will be done using central laboratory services. Venous whole blood will be collected in appropriate syringes provided by the sponsor through the assigned central laboratory. Details regarding centrifuge, processing, storage and shipment of samples will be determined by the central laboratory in accordance with the sponsor. The investigators will be informed and instructed by the central laboratory and detailed documentation will be included in the ISF.

Additionally, all patients will have intermediate liver function monitoring visits (AST, ALT and bilirubin) when the interval between 2 regular visits exceeds 8 weeks. At these visits blood may be collected at the investigational site, primary physician (GP or Pulmonologist) or external laboratory. However analysis will still be performed by the central laboratory.

In case of liver enzymes elevation, close monitoring must be ensured by the investigator (please refer to [Section 4.2.1.2](#)).

For patients continuing treatment with nintedanib within this trial after the database lock for the final analysis, laboratory tests will no longer be part of the trial related procedures. However investigators are encouraged to monitor liver function locally according to the recommendations provided in the Investigators Brochure and to manage liver enzyme elevations according to the recommendations provided in [section 4.2.1.2](#) Management of liver enzyme elevations.

Proprietary confidential information.

© 2017 Boehringer Ingelheim International GmbH or one or more of its affiliated companies. All rights reserved.

This document may not - in full or in part - be passed on, reproduced, published or otherwise used without prior written permission.

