2.3 BENEFIT - RISK ASSESSMENT

Nintedanib has shown robust, reproducible, statistically significant, and clinically meaningful effects on the decline in lung function as measured by FVC. In two large, international, placebo-controlled phase III trials of identical design, nintedanib 150 mg bid statistically and clinically significantly reduced the annual rate of decline in FVC over 52 weeks compared with placebo indicating a relative difference of approximately 50% between nintedanib and placebo. This effect of nintedanib is considered consistent with slowing disease progression as measured by FVC.

The risks of treatment with nintedanib are primarily related to the gastrointestinal tract (nausea, vomiting, diarrhoea, abdominal pain) and to increases in liver enzymes (AST, ALT, ALKP, gamma-GT) and bilirubin. Also weight decrease and decreased appetite have frequently been reported in studies with nintedanib. Moreover, based on experience with other tyrosine kinase inhibitors, impairment of immune and of kidney function, intestinal perforations, increases in blood pressure as well as potential bleeding and thrombotic events should be carefully monitored and evaluated in clinical trials. In patients who develop severe symptoms of gastrointestinal toxicity not amenable to symptomatic treatment with standard measures, severe liver enzyme elevations, severe drug-related infections, or uncontrolled hypertension, treatment with nintedanib must be discontinued and appropriate therapeutic measures taken (refer to [Section 4.2.1.1](#)). Liver enzymes must be followed closely during treatment with nintedanib.

Proprietary confidential information.

© 2017 Boehringer Ingelheim International GmbH or one or more of its affiliated companies. All rights reserved.

This document may not - in full or in part - be passed on, reproduced, published or otherwise used without prior written permission.

The dose of nintedanib must be reduced to 100mg bid, or nintedanib must be discontinued in the event of hepatic toxicity and further treatment withheld until recovery of the abnormal laboratory parameters (refer to [Section 4.2.1.2](#)).

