3.3.4 Removal of patients from therapy or assessments

3.3.4.1 Removal of individual patients

The treatment with nintedanib has to be permanently discontinued in the following circumstances:

- Liver function impairment (refer to [Section 10.1](#)):
 - ALT or AST \geq 8 fold ULN.
 - ALT or AST \geq 3 fold ULN for more than 2 weeks despite dose reduction.
 - ALT or AST \geq 3 fold ULN and total bilirubin $>$ 1.5 fold ULN.
 - ALT or AST \geq 3 fold ULN and INR $>$ 1.5.
 - ALT or AST \geq 3 fold ULN with the appearance of fatigue, nausea, vomiting, right upper abdominal quadrant pain or tenderness, fever, rash, and/or eosinophilia ($>$ 5%).
- Diarrhoea: reoccurrence of diarrhoea ($>$ 4 stools/day) for 8 or more consecutive days despite dose reduction and supportive care as described in [Section 4.2.1.1](#).
- Pregnancy (refer to [Section 5.3.7](#)).
- Planned usage of a specific investigational drug (refer to [Section 4.2.2.1](#)).
- Treatment interruption. Treatment interruption is acceptable in certain cases and for a defined period which are described in [Section 4.2.1](#).

Similar to the parent study, in the following cases withdrawal of study drug is highly recommended. Only in special circumstances, the investigator, upon thorough assessment of all available clinical data, and taking into consideration the potential risks associated with administration of nintedanib, may decide not to withdraw the patient, even though one or more of the below mentioned criteria are fulfilled. However, in such a case, continuation of study treatment should be discussed with the patient, and the decision documented in the source data.

Proprietary confidential information.

© 2017 Boehringer Ingelheim International GmbH or one or more of its affiliated companies. All rights reserved.

This document may not - in full or in part - be passed on, reproduced, published or otherwise used without prior written permission.

- Planned major surgery, including any major abdominal or intestinal surgery.
- Patients who require full-dose therapeutic anticoagulation (e.g. vitamin K antagonists, dabigatran, heparin, hirudin), or high-dose antiplatelet therapy.
- Major thrombo-embolic events e.g. stroke, deep vein thrombosis, pulmonary embolism, myocardial infarction.
- Increased risk of bleeding e.g. haemorrhagic CNS event, gross / frank haemoptysis or haematuria, active gastro-intestinal bleeding or ulcers.

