4.2.1.2 Management of liver enzyme elevation

The guidelines for managing liver enzyme elevations are the same as is in the parent protocols. The following procedures are based on the *FDA Guidance for Industry. Drug-Induced Liver Injury: Premarketing Clinical Evaluation (P09-12413)*.

ALT or AST > 1.5 fold ULN and < 3 fold ULN

- Continue as planned

ALT or AST \geq 3 fold ULN and < 5 fold ULN with no signs of severe liver damage

- Reduce to 100 mg bid or interrupt treatment (to be decided by investigator, based on individual risk assessment)
- Re-test ALT and AST, as well as alkaline phosphatase, total bilirubin and eosinophils within 48 to 72 hours, then at approximately 7 days, then at approximately 2 weeks, and assess signs of severe liver damage:
 - If ALT and AST < 3 fold ULN after 2 weeks, return to initial dose if reduced, restart at reduced dose if interrupted. Monitor lab (see above) every 2 weeks for at least 8 weeks.
 - If ALT and/or AST \geq 3 fold ULN after 2 weeks or any time thereafter, permanently discontinue study medication.

ALT or AST \geq 5 fold ULN and < 8 fold ULN with no signs of severe liver damage

- Interrupt treatment.
- Re-test ALT and AST, as well as alkaline phosphatase, total bilirubin and eosinophils within 48 to 72 hours, then at approximately 7 days, then at approximately 2 weeks, and assess signs of severe liver damage:
 - If AST and ALT < 3 fold ULN after 2 weeks, restart at reduced dose. Monitor lab (see above) every week for 4 weeks, then every 2 weeks for at least 8 weeks.
 - If AST and/or ALT \geq 3 fold ULN after 2 weeks or any time thereafter, permanently discontinue study medication.

ALT or AST \geq 8 fold ULN or signs of severe liver damage

- Permanently discontinue study medication.

Proprietary confidential information.

© 2017 Boehringer Ingelheim International GmbH or one or more of its affiliated companies. All rights reserved.

This document may not - in full or in part - be passed on, reproduced, published or otherwise used without prior written permission.

- Patients showing these lab abnormalities need to be followed up according to [Section 10.1.1](#) of this clinical trial protocol and the “DILI checklist” provided in ISF.

Signs of severe liver damage are defined as:

Increase of liver transaminases (ALT or AST \geq 3 fold ULN) and:

- appearance of fatigue, nausea, vomiting, right upper abdominal quadrant pain or tenderness, fever, rash, and/or eosinophilia ($>$ 5%); or

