- Total bilirubin $>$ 1.5 fold ULN; or
- INR $>$ 1.5;

Please refer to [Section 10.1](#) for more detailed instructions.

Immediately refer to [Section 5.3.6.1](#) in case AST and/or ALT \geq 3 fold ULN is combined with total bilirubin \geq 2 fold ULN.

Initial assessment of liver enzyme elevation should be performed at the investigational site. Blood samples for additional monitoring may be collected at the investigational site, primary physician (GP or Pulmonologist) or external laboratory with specific study kits and sent to the central laboratory for analysis.

For patients continuing treatment with nintedanib within this trial after the database lock for the final analysis, the liver function monitoring is to be done locally in case of liver enzyme elevations.

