6.2.5. Period after the database lock for the final analysis

After the database lock for the final analysis (refer to [section 7.3](#)) and once consent has been provided, the remaining patients in the trial (patients without access to nintedanib outside the clinical trial) will be offered continuation of treatment within the trial. This period will consist of study visits every 16 weeks (± 2 weeks) where the following procedures will be conducted:

- Assessment of adverse events and concomitant therapy since last visit;
- Dispensing of trial drug.

Patients will continue to receive treatment until they meet a reason for discontinuation (refer to [section 3.3.4](#)) or until access to nintedanib is obtained outside the clinical trial.

Dose reductions, interruptions and re-escalations are possible at any time during the scheduled study visits or between visits to manage adverse events.

End of treatment and follow up visits have to be performed to conclude the treatment period and trial participation.

Study procedures per visit are described in the [Flow Chart](#) for patients who continue treatment after the database lock for the final analysis. Investigators are encouraged to monitor liver function locally according to the recommendations provided in the Investigators Brochure.

Only Adverse Events, Concomitant medications and reason of trial drug discontinuation and trial completion will be collected in the eCRF.

Proprietary confidential information.

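### After the final lock, one sentence in Protocol 5.3.3 words the management of a known liver enzyme elevation as optional, in conflict with 2.3, 3.3.4.1, 4.2.1.2 and Table 10.1:1

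*Protocol*

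**What the plan says.** Amendment 3 created a reduced schedule for patients without other access to nintedanib. Laboratory tests stop being trial procedures, and the post-lock flow chart has no laboratory row. For these patients Section 5.3.3 adds that "investigators are encouraged to monitor liver function locally according to the recommendations provided in the Investigators Brochure and to manage liver enzyme elevations", pointing to 4.2.1.2 for what it calls recommendations. A general rule earlier in the same section, with no time limit, reads: "In case of liver enzymes elevation, close monitoring must be ensured by the investigator".

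Other sections use firmer language and contain no post-lock exception:

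- Section 2.3: "The dose of nintedanib must be reduced to 100mg bid, or nintedanib must be discontinued in the event of hepatic toxicity", with a reference to 4.2.1.2.
- Section 3.3.4.1, introducing a list that begins with liver criteria and refers to Section 10.1: "The treatment with nintedanib has to be permanently discontinued in the following circumstances".
- Section 4.2.1.2, at 3 to <5 times ULN: "Reduce to 100 mg bid or interrupt treatment (to be decided by investigator, based on individual risk assessment". At 5 to <8 times it says to interrupt. At 8 times or more, or with signs of severe liver damage, it says to stop permanently. Table 10.1:1 repeats these bands.
- Section 4.2.1.2, in its own post-lock sentence: "the liver function monitoring is to be done locally in case of liver enzyme elevations".
- Section 6.2.5, with a reference to 3.3.4: "Patients will continue to receive treatment until they meet a reason for discontinuation".

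On data capture after the lock, 6.2.5 says: "Only Adverse Events, Concomitant medications and reason of trial drug discontinuation and trial completion will be collected in the eCRF".

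**The concern.** In the 5.3.3 sentence the verb *encouraged* governs both monitoring and managing. Encouraging routine local tests fits a deliberate reduction in scheduled procedures. Encouraging action on an elevation already found is different, because other sections require that action.

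What is at stake is how clearly a patient-safety instruction reads for a known risk. Section 1.2 reports AST and/or ALT of at least 3 times ULN in 4.9% and 5.2% of nintedanib patients in the two parent trials, against 0.5% and 0.9% on placebo. These are background rates over 52 weeks and do not estimate what happens after the lock.

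A second, smaller question is whether the liver-injury work-up in 10.1.1.2 still fits a period in which monitoring is local and the eCRF is reduced.

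**Working it through.** No arithmetic applies, and the plan gives no figure to reproduce. The check sets the clauses side by side.

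1. **Force of each clause after the lock.** Monitoring of a known elevation is mandatory in 5.3.3 (general rule) and in 4.2.1.2 (to be done locally), so there is no conflict on monitoring. Management of a known elevation is encouraged in 5.3.3 but required in 2.3, 4.2.1.2 and Table 10.1:1. The conflict is there.

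2. **What 6.2.5 carries forward.** It keeps the 3.3.4 reasons for discontinuation. The liver entries in 3.3.4.1 are all permanent stops:
   - at least 8 times ULN;
   - at least 3 times ULN for more than two weeks despite dose reduction;
   - at least 3 times ULN with bilirubin above 1.5 times ULN, with INR above 1.5, or with listed symptoms or eosinophilia.

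   The top band of 4.2.1.2 is therefore fully covered. So are complicated elevations from 3 times upward. The first step for an uncomplicated elevation of 3 to <8 times ULN is not in the 3.3.4.1 list. It stands in 4.2.1.2, is made obligatory by 2.3, and is repeated in Table 10.1:1.

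3. **A test case.** Take a patient on 150 mg bid with a local ALT of 6 times ULN, normal bilirubin and INR, no symptoms and no eosinophilia. Under 4.2.1.2 and Table 10.1:1, treatment is interrupted. The patient meets no listed criterion of 3.3.4.1 that day. If the site relies on 5.3.3 and leaves the dose unchanged, the two-week criterion in 3.3.4.1 is literally not met either, because it presupposes a dose reduction. The two-week stop without that condition is in 4.2.1.2 and Table 10.1:1.

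4. **Was optional management intended?** Nothing says so. Section 6.2.5, added by the same amendment, uses encouragement for monitoring only. The reason given in Section 11 for the 5.3.3 addition is confined to local monitoring. The post-lock sentence in 4.2.1.2 changes where monitoring is done and leaves every action band as it was. SAP Table 6.2: 1 classes three related failures as important safety violations: dose changes outside CTP 4.2.1 (C6), failure to stop when 3.3.4.1 is met (C7), and inadequate follow-up of a liver elevation (F1).

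5. **The work-up in 10.1.1.2.** Section 4.2.1.2 requires it at 8 times ULN or more, or with signs of severe liver damage. The additional sample for the reflex panel goes to the central laboratory. The local fallback names ALT, AST and bilirubin only. The work-up is to be reported through the CRF, but the post-lock eCRF described in 6.2.5 has no laboratory or work-up content. Section 10.1.1.2 was not adapted to the post-lock period.

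**The case against.** The strongest reply is that the plan already settles the matter. The 2.3 sentence ends with a reference to 4.2.1.2, so the thresholds come with the obligation. Section 3.3.4.1 refers to Section 10.1, whose table repeats the reduce-or-interrupt and interrupt instructions. The section that governs management, 4.2.1.2, was itself amended for post-lock patients without softening any action. A site would have to let one clause in a laboratory section override all of these. In the 3 to <5 times band, the choice between reducing and interrupting is the investigator's in any case.

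Most of this stands. A reader might infer that mandatory liver rules lapse after the lock; the documents do not support that. They also do not support reading the reduced testing schedule as an oversight. What the reply does not remove is the contradiction. Section 5.3.3 is explicit, is addressed to exactly these patients, and labels the 4.2.1.2 actions recommendations.

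On the work-up, a reader might infer that the panel has no laboratory after the lock and that its results have no route to the sponsor. Neither is stated. No text withdraws the central laboratory. Clinically relevant laboratory changes are still recorded as adverse events (5.3.6.1). Transaminases of at least 3 times ULN with bilirubin of at least 2 times ULN remain a protocol-specified significant event, sent on the SAE form (5.3.6.1, 5.3.7). Section 10.1.1.2 also requires local fallback results and confirmed-case panel results to be made available to the sponsor. Only the misalignment remains.

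**Conclusion.** The wording conflict is real and should be corrected. It is one sentence at odds with rules that remain in force. Its practical reach is the first dose reduction or interruption for an uncomplicated ALT or AST of 3 to <8 times ULN, together with the two-week criterion of 3.3.4.1 that presupposes that step. Stops at 8 times ULN or more, stops for complicated elevations, and monitoring of a known elevation are all secured.

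The 10.1.1.2 point is secondary. The panel laboratory and the CRF instruction do not fit local monitoring and the reduced eCRF. Whether the central laboratory stays available after the lock is not stated, and the site-file DILI checklist, which may bear on this, is not among the documents.

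The size cannot be put as a patient or event count, because the number continuing after the lock is not given. No planned analysis is affected: under Protocol 7.3 and 7.4 the main analyses use data up to the third interim lock, and later data are only listed.

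**What to change.** - **Section 5.3.3.** Keep encouragement for routine local monitoring under the Investigator's Brochure, and end it there. Then add: *Once a local liver result is known, the criteria of Section 3.3.4.1 and the actions of Section 4.2.1.2 and Table 10.1:1 apply unchanged.*
- **Section 6.2.5.** Add a cross-reference to that sentence.
- **Section 10.1.1.2.** State which laboratory runs the panel after the lock, with local testing where the central laboratory is not available. State that results accompany the SAE form if the event is serious or protocol-specified significant, and otherwise the adverse event record. The last clause is needed because 8 times ULN alone triggers the work-up but is not by itself a protocol-specified significant event. The sponsor should confirm which panel items local laboratories can run.

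Section 2.3 needs no change. The cost is about two sentences each in 5.3.3 and 10.1.1.2 and one cross-reference, with the approvals that any amendment needs under Section 8.1. There is no new visit, scheduled test or eCRF page. The drawback is that a local work-up may be less uniform than the central panel, and some items may not be available locally.
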